In this study, 72 healthy adult smokers will be randomized. This will provide more than 90% power to demonstrate a reduction for all BoExp tested in the primary objective in the combined P4M3 arms compared to the CIG arm, using a one-sided two-sample t-test with 2.5% type I error probability. This assumes, based on a previous similar study conducted by PMP (see [ClinicalTrials.gov](https://clinicaltrials.gov/ct2/show/study/NCT01959932) Identifier: NCT01959932), that the geometric mean ratio (GM) and the related geometric coefficient of variation (GCV) of the ratio between the combined P4M3 arms and the CIG arm are the following:

- GMR = 23.45% and GCV = 16.84% for COHb at Day 5,
- GMR = 41.63% and GCV = 26.10% for 3-HPMA at Day 5,
- GMR = 13.16% and GCV = 6.5% for 2-CyEMA at Day 5,
- GMR = 43.54% and GCV = 5.2% for Total NNAL at Day 5.

Investigational Products; Dose; and Mode of Administration:

Investigational Product:

P4M3 Battery Units and Cartridges will be provided by the Sponsor.

The following P4M3 variants will be investigated:

Name	Nicotine concentration	e-liquid flavor	Name in study
P4M3 Classic Auburn	3.5 %	Tobacco	CA35
P4M3 Classic Menthol	3.5 %	Menthol	CM35

Confidentiality Statement

Data and information contained in this document are considered to constitute trade secrets and confidential commercial information, and the legal protections provided to such trade secrets and confidential information are hereby claimed under the provisions of applicable law. No part of this document may be publicly disclosed without the written consent of Philip Morris Products S.A

Comparator:

CIG arm: Subject's own preferred brand of commercially available, regular or mentholated CIG (not provided by the Sponsor).

Reference:

Not applicable.

Duration of Study:

The entire study duration per subject will be 11 to 38 days. This will include a Screening period of up to 28 days prior to Admission (Day -30 to Day -3), followed by a 7-day confinement period (Day -2 to Day 5, followed by Discharge on Day 6), and a 3-day Safety follow-up period.

The End of the study (EOS) for a subject is defined as the completion of the 3-day Safety follow-up period either after the Discharge at Day 6, or after the early termination of the subject. The end of the whole study corresponds to the EOS of the last subject.

Statistical Methods:**Analysis Sets:**

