12.9.4 Determination of Sample Size and Power Consideration

In this study, 72 subjects will be randomized as follows:

- 36 in combined P4M3 arms (18 in CA35 and 18 in CM35),
- 18 in CIG arm,
- 18 in SA arm.

Based on four previous similar studies conducted by PMI on the tobacco heating system (another alternative product to cigarette developed by PMI which is likely to be less risky than cigarette; ClinicalTrials.gov identifiers are NCT01970995, NCT01989156, NCT01959932, and NCT01970982, respectively), [Table 16](#) contains estimates of geometric mean ratios (GMR) and associated coefficients of variations (GCV) for the (adjusted) contrast of a tobacco heating system against CIG. The effect of P4M3 is expected to be similar (or better) on the BoExp selected in this study than this tobacco heating system. In addition, based on these studies, up to 15% of missing values may be expected for various reasons (e.g., withdrawals, mis-randomization, etc.).

Using the statistics displayed in [Table 16](#), the sample size planned for this study accounting for 15% of missing values (resulting in 30 and 15 subjects in P4M3 combined and CIG arms, respectively), and a one-sided two-sample t-test (on the log-scale) with 2.5% type I error probability, the estimated power for each BoExp is displayed in [Table 16](#). By multiplying the power for each individual BoExp over the four to be tested in the primary hypothesis (per study), a global estimate of power is also obtained.

Confidentiality Statement

Data and information contained in this document are considered to constitute trade secrets and confidential commercial information, and the legal protections provided to such trade secrets and confidential information are hereby claimed under the provisions of applicable law. No part of this document may be publicly disclosed without the written consent of Philip Morris Products S.A.

Note that 10'000 simulations of one-sided two-sample t-test were also conducted to determine the 90 percentiles of the (upper) half-width of the 97.5%-confidence interval (CI) of the ratio between P4M3 and CIG, as well as the 90 percentiles of the upper bounds of these CIs. These are also displayed in [Table 16](#). These provide indications on the expected precision on the estimates of the ratios.

Table 16 Power Computations for Primary Objective

NCT (Region)	Endpoint	GMR (%)	GCV (%)	Power	Overall Power	90%iles of the upper half-width of CI (%)	90%iles of the upper bound of CI (%)

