1970995 (JP)	2CyEMA	18.23	32.43	>99%	>99%	4.9	25.4
	3-HPMA	50.67	32.72	>99%		13.8	71.0
	COHb	44.94	17.24	>99%		6.0	53.8
	Total NNAL	43.69	26.09	>99%		9.2	57.1
1989156 (US)	2CyEMA	17.23	42.01	>99%	>99%	6.2	26.3
	3-HPMA	45.77	36.45	>99%		14.1	66.3
	COHb	38.14	26.5	>99%		8.2	50.3
	Total NNAL	43.81	40.7	>99%		15.3	65.9
1959932 (EU)	2CyEMA	13.16	34.41	>99%	>99%	3.8	18.7
	3-HPMA	41.63	26.1	>99%		8.7	54.4
	COHb	23.45	16.84	>99%		3.1	28.0
	Total NNAL	43.54	27.13	>99%		9.6	57.5
1970982 (JP)	2CyEMA	21.21	43.16	>99%	>99%	7.9	32.7
	3-HPMA	52.86	39.57	>99%		17.8	78.9
	COHb	47.1	16.08	>99%		5.8	55.6
	Total NNAL	49.03	42.51	>99%		18.0	75.3

[Table 16](#) shows that the power of this study for the primary objective is expected to be at least 99%.

A similar reasoning and assumptions for the 1st key secondary objective can be made. [Table 17](#) displays the power estimates for the 1st key secondary hypothesis with a power of at least 99%.

Table 17 Power Computations for 1st Key Secondary Objective

NCT (Region)	Endpoint	GMR (%)	GCV (%)	Power	Overall Power	90%iles of the upper half-width of CI (%)	90%iles of the upper bound of CI (%)
1970995 (JP)	3-HMPMA	43.06	35.59	>99%	>98%	12.9	62.0
	3-OH-B[a]P	27.19	43.93	>99%		10.4	42.0
	S-PMA	10.97	46.63	>99%		4.5	17.4
	Total NNN	27.02	61.84	>99%		15.5	49.1
1989156 (US)	3-HMPMA	38.26	53.56	>99%	>98%	18.4	64.6
	3-OH-B[a]P	28.94	54.77	>99%		14.3	49.4
	S-PMA	12.58	69.68	>99%		8.4	24.4
	Total NNN	14.06	78.93	>99%		10.8	29.1
1959932 (EU)	3-HMPMA	22.54	30.76	>99%	>98%	5.7	30.9
	3-OH-B[a]P	27.5	46.17	>99%		11.1	43.5
	S-PMA	5.99	37.3	>99%		1.9	8.8

Confidentiality Statement

Data and information contained in this document are considered to constitute trade secrets and confidential commercial information, and the legal protections provided to such trade secrets and confidential information are hereby claimed under the provisions of applicable law. No part of this document may be publicly disclosed without the written consent of Philip Morris Products S.A.

NCT (Region)	Endpoint	GMR (%)	GCV (%)	Power	Overall Power	90%iles of the upper half-width of CI (%)	90%iles of the upper bound of CI (%)
	Total NNN	24.12	95.15	>99%		22.9	55.7
1970982 (JP)	3-HMPMA	37.71	49.07	>99%	>98%	16.4	61.6
	3-OH-B[a]P	29.99	52.2	>99%		14.0	50.2
	S-PMA	15.68	49.76	>99%		6.9	25.6
	Total NNN	30.06	67.69	>99%		19.2	57.4

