For the key secondary objectives 2 to 5, a similar reasoning is applied, but this time, a sample of size of 15 for the P4M3 (CA35 or CM35) arms needs to be used and 15 subjects in the CIG arm (with 15 subjects) (Table 18 and Table 19). As per Table 18 and Table 19 the power was of at least of 99% for each BoExp in the previous studies.

By multiplying the power for each objective ($\approx 99\%$) across all 6 objectives (1 primary + 5 key secondary), the power for all objectives altogether is then estimated to be at least 94% ($= 0.94 \approx 0.99^6$, assuming independence of the 6 objectives, each with a 99% power).

Table 18 Power Computations for Key Secondary Objectives 2 & 4

NCT (Region)	Endpoint	GMR (%)	GCV (%)	Power	Overall Power	90%iles of the upper half-width of CI (%)	90%iles of the upper bound of CI (%)
1970995 (JP)	2CyEMA	18.23	32.43	>99%	>95%	6.1	26.9
	3-HPMA	50.67	32.72	>99%		17.2	75.2
	COHb	44.94	17.24	>99%		7.3	55.4
	Total NNAL	43.69	26.09	>99%		11.3	59.7
1989156 (US)	2CyEMA	17.23	42.01	>99%	>95%	7.8	28.3
	3-HPMA	45.77	36.45	>99%		17.5	70.7
	COHb	38.14	26.5	>99%		10.1	52.7
	Total NNAL	43.81	40.7	>99%		19.3	71.0
1959932 (EU)	2CyEMA	13.16	34.41	>99%	>95%	4.7	19.8
	3-HPMA	41.63	26.1	>99%		10.8	56.9
	COHb	23.45	16.84	>99%		3.7	28.8
	Total NNAL	43.54	27.13	>99%		11.9	60.4
1970982 (JP)	2CyEMA	21.21	43.16	>99%	>95%	9.9	35.0
	3-HPMA	52.86	39.57	>99%		22.4	84.4
	COHb	47.1	16.08	>99%		7.1	57.2
	Total NNAL	49.03	42.51	>99%		22.5	80.9

Table 19 Power Computations for Key Secondary Objectives 3 & 5

NCT (Region)	Endpoint	GMR (%)	GCV (%)	Power	Overall Power	90%iles of the upper half-width of CI (%)	90%iles of the upper bound of CI (%)
1970995 (JP)	3-HMPMA	43.06	35.59	>99%	>94%	16.0	65.9
	3-OH-B[a]P	27.19	43.93	>99%		13.0	45.2
	S-PMA	10.97	46.63	>99%		5.6	18.9
	Total NNN	27.02	61.84	>99%		19.8	54.2
1989156 (US)	3-HMPMA	38.26	53.56	>99%	>94%	23.2	70.4
	3-OH-B[a]P	28.94	54.77	>99%		18.2	54.2
	S-PMA	12.58	69.68	>99%		10.7	27.3

Confidentiality Statement

Data and information contained in this document are considered to constitute trade secrets and confidential commercial information, and the legal protections provided to such trade secrets and confidential information are hereby claimed under the provisions of applicable law. No part of this document may be publicly disclosed without the written consent of Philip Morris Products S.A

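### Do the conflicting planning figures in the protocol synopsis and SAP Table 11 undermine the sample size?

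*Protocol*

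**What the plan says.** The synopsis (Sample Size) names study NCT01959932 as its source and lists a geometric mean ratio (GMR) and a geometric coefficient of variation (GCV) for each primary biomarker. Two entries are "GMR = 13.16% and GCV = 6.5% for 2-CyEMA at Day 5" and "GMR = 43.54% and GCV = 5.2% for Total NNAL at Day 5". The other two are COHb (23.45%, 16.84%) and 3-HPMA (41.63%, 26.10%). On power, it says "This will provide more than 90% power to demonstrate a reduction for all BoExp tested in the primary objective".

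Protocol section 12.9.4 uses four earlier studies, of which NCT01959932 is one. The test is a "one-sided two-sample t-test (on the log-scale) with 2.5% type I error probability", with numbers reduced for dropout: "up to 15% of missing values may be expected for various reasons", "resulting in 30 and 15 subjects in P4M3 combined and CIG arms, respectively". For the single-variant comparisons, "a sample of size of 15 for the P4M3 (CA35 or CM35) arms needs to be used and 15 subjects in the CIG arm". Table 16 gives GCVs of 34.41% (2-CyEMA) and 27.13% (total NNAL) for NCT01959932, and the section says that the table "shows that the power of this study for the primary objective is expected to be at least 99" per cent. SAP section 6 repeats these tables.

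For study NCT01970982, SAP Table 11 shows S-PMA with GMR 45.68 and total NNN with GCV 57.69. Protocol Tables 17 and 19 and SAP Table 9 show 15.68 and 67.69.

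**The concern.** These figures are the stated effect and variability assumptions behind the sample size. In the synopsis, two of four co-primary endpoints carry a GCV about one fifth of the one in the body of the protocol, for the same study and the same GMR. On the log scale that is roughly a 26-fold smaller variance. If the sample size rested on those figures, the power claim could be far too optimistic, and success requires all four endpoints to be significant.

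The SAP entries raise a similar doubt. A GMR of 45.68 means a 54% reduction in S-PMA, where 15.68 means 84%. Key secondary objectives 3 and 5 depend on these rows, and the fixed sequence stops at the first failure.

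The synopsis also appears to make a different power claim (above 90%, one study) from section 12.9.4 (at least 99%, four studies).

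**Working it through.** **Inputs.** One-sided alpha 0.025; 30 vs 15 evaluable subjects for the combined arms and 15 vs 15 for a single variant (section 12.9.4); GMR and GCV from the tables and the synopsis.

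**Formulas.** Log-scale SD: s = √ln(1 + GCV²). Standard error: SE = s·√(1/n₁ + 1/n₂). Noncentrality: δ = −ln(GMR)/SE. Power is the probability that a noncentral t with n₁ + n₂ − 2 degrees of freedom exceeds the critical value (2.017 for 43 df, 2.048 for 28 df). The 90th percentiles of the upper half-width and upper bound of the confidence interval come from 200,000 simulated trials per entry.

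**Synopsis against Table 16 (30 vs 15, √(1/30 + 1/15) = 0.3162).**

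| Endpoint | GCV | s | SE | δ | Power | Simulated half-width / bound | Table 16 prints |
|---|---|---|---|---|---|---|---|
| 2-CyEMA, GMR 13.16% | 34.41% | 0.3345 | 0.1058 | 2.028/0.1058 = 19.2 | >99.99% | 3.8 / 18.7 | 3.8 / 18.7 |
| 2-CyEMA | 6.5% | 0.0649 | 0.0205 | 98.8 | >99.99% | 0.6 / 14.1 | – |
| Total NNAL, GMR 43.54% | 27.13% | 0.2665 | 0.0843 | 0.8315/0.0843 = 9.9 | >99.99% | 9.6 / 57.6 | 9.6 / 57.5 |
| Total NNAL | 5.2% | 0.0520 | 0.0164 | 50.6 | >99.99% | 1.7 / 46.0 | – |

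The printed precision columns match the Table 16 GCVs and not the synopsis GCVs. The variance ratios are (0.3345/0.0649)² ≈ 26.5 and (0.2665/0.0520)² ≈ 26.3, yet δ is far above the critical value in every row.

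**SAP Table 11 against protocol Table 19 (15 vs 15, √(2/15) = 0.3651).**

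| Entry, study NCT01970982 | GMR / GCV | SE | δ | Power | Simulated half-width / bound | Both tables print |
|---|---|---|---|---|---|---|
| S-PMA, protocol | 15.68 / 49.76 | 0.1717 | 1.853/0.1717 = 10.8 | >99.99% | 8.7 / 27.9 | 8.8 / 27.9 |
| S-PMA, SAP Table 11 | 45.68 / 49.76 | 0.1717 | 0.7835/0.1717 = 4.56 | 99.3% | 25.5 / 81.4 | 8.8 / 27.9 |
| Total NNN, protocol | 30.06 / 67.69 | 0.2243 | 1.202/0.2243 = 5.36 | 99.93% | 24.6 / 63.7 | 24.6 / 63.8 |
| Total NNN, SAP Table 11 | 30.06 / 57.69 | 0.1957 | 1.202/0.1957 = 6.14 | >99.99% | 20.1 / 58.0 | 24.6 / 63.8 |

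The S-PMA row in SAP Table 11 also contradicts itself: the 90th percentile of the upper bound (27.9) lies below the assumed ratio (45.68). The calculation behind that row must have used 15.68.

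**The two power statements.** At least 99% satisfies above 90%, and the synopsis study is one of the four in section 12.9.4. The two statements are compatible.

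**A possible source of the synopsis values.** (0.0649/0.3345)² = 0.0377 and (0.0520/0.2665)² = 0.0380. Both odd GCVs are what a standard error of the log ratio would give if 1/n₁ + 1/n₂ were about 0.038, for example with arms of about 80 and 40 (1/80 + 1/40 = 0.0375). The documents do not give that study's arm sizes, so this is only an inference. If it is right, the synopsis mixes two scales in one list and does not report a different estimate of variability.

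**The case for a change.** The strongest case for acting is that a protocol should state its planning assumptions correctly, and the synopsis is the part most widely read. One list there carries two GCVs that agree with Table 16 and two that do not. Describing the figures as belonging to the ratio does not rescue the small ones, because the COHb and 3-HPMA values beside them are the Table 16 figures. SAP section 7, which lists departures from the protocol, mentions no change in planning values. The corrections would touch four numbers.

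It stands that the entries disagree and that the tables show which value was used. Three parts do not stand. The power statements do not conflict. The synopsis states no precision, so none in it fails to reproduce; planned precision is given only in the tables, where it does reproduce. And the SAP already shows 15.68 and 67.69 in Table 9. The two SAP Table 11 entries differ from the protocol by one leading digit each, so an error in reading the PDF cannot be excluded without looking at the source page.

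**Conclusion.** This is a clerical inconsistency, and no change to the plan follows. The power calculations in protocol section 12.9.4 and SAP section 6 rest on the inputs that reproduce their own printed results: 34.41%, 27.13%, 15.68 and 67.69. Under every version of the disputed figures, power is at least 99.3% for the endpoint concerned, and above 99.99% for the two primary endpoints in the synopsis. The 72 subjects, the stated power, the model, the alpha, the testing sequence and the success criteria are the same whichever figure is read. None of these planning values enters the analysis of the trial's data.

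This conclusion rests on the plan's own assumptions: log-normal endpoints, 15% missing values, and effects like those of the earlier tobacco heating system studies. Whether those effects carry over to P4M3 is a separate question that the misprints do not touch. If either document is reopened for another reason, the four entries can be tidied then, after checking the two in SAP Table 11 against the source page.

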Confidentiality Statement

Data and information contained in this document are considered to constitute trade secrets and confidential commercial information, and the legal protections provided to such trade secrets and confidential information are hereby claimed under the provisions of applicable law. No part of this document may be publicly disclosed without the written consent of Philip Morris Products S.A

Abbreviations and Definitions of Terms

Abbreviations

2-CyEMA	2-Cyanoethyl mercapturic acid N -Acetyl- S -(2-cyanoethyl)-L-cysteine
2-HPMA	2-hydroxypropylmercapturic acid
3-HMPMA	3-hydroxy-1-methylpropylmercapturic acid
3-HPMA	3-hydroxypropylmercapturic acid
3-OH-B[a]P	3-hydroxybenzo(a)pyrene
ABOUT	Assessment of behavioral outcomes related to tobacco and nicotine products
AE	Adverse event
BMI	Body mass index
BoExp	Biomarker of exposure
CA35	P4M3 Gen 2.0 variant Classic Auburn 3.5% nicotine
CAF	Caffeine
CI	Confidence interval
CIG	Conventional cigarette (smoking)
CM35	P4M3 Gen 2.0 variant Classic Menthol 3.5% nicotine
CO	Carbon monoxide
COHb	Carboxyhemoglobin
CRF	Case report form
CRO	Contract research organization
CSR	Clinical study report
CTMS	Clinical trial management system
CV	Coefficient of variation
CYP1A2	Cytochrome P450 1A2
DHPMA	2,3-dihydroxypropylmercapturic acid
DMP	Data management plan
ECG	Electrocardiogram
EOS	End of study
FAS	Full analysis set
FDA	Food and Drug Administration
FEF	Forced expiratory flow

Confidentiality Statement

Data and information contained in this document are considered to constitute trade secrets and confidential commercial information, and the legal protections provided to such trade secrets and confidential information are hereby claimed under the provisions of applicable law. No part of this document may be publicly disclosed without the written consent of Philip Morris Products S.A.

FEV ₁	Forced expiratory volume in 1 second
FTND	Fagerström test for nicotine dependence (revised version)
FVC	Forced vital capacity
GCV	Geometric coefficient of variation
GCP	Good Clinical Practice
GMR	Geometric mean ratio
HBV	Hepatitis B virus
HCV	Hepatitis C virus
HIV	Human immunodeficiency virus
HPHC(s)	Harmful and potentially harmful constituent(s)
HPT	Human puffing topography
IB	Investigator's Brochure
ICF	Informed consent form
ICH	International Conference on Harmonization
IP	Investigational product
IEC	Independent Ethics Committee
IxRS	Interactive web/voice response system
LLN	Lower limit of the normal range
LLOQ	Lower limit of quantification
MCEQ	Modified cigarette evaluation questionnaire
MDEDR	Miniaturized detachable external data recorder
MedDRA	Medical dictionary for regulatory activities
MHBMA	Monhydroxybutenyl mercapturic acid
NEQ	Nicotine equivalents
NNAL	4-(methylnitrosamino)-1-(3-pyridyl)-1-butanol
NNK	4-(methylnitrosamino)-1-(3-pyridyl)-1-butanone
NNN	N-nitrosornicotine
NRT	Nicotine replacement therapy
PMP	Philip Morris Products S.A.
PP	Per protocol set
PI	Principal investigator
PX	Paraxanthine
QC	Quality control
SA	Smoking abstinence

Confidentiality Statement

Data and information contained in this document are considered to constitute trade secrets and confidential commercial information, and the legal protections provided to such trade secrets and confidential information are hereby claimed under the provisions of applicable law. No part of this document may be publicly disclosed without the written consent of Philip Morris Products S.A.

SAE	Serious adverse event
SAP	Statistical analysis plan
SHM	Sample handling manual
SOP	Standard operating procedure
S-PMA	S -phenylmercapturic acid
TNP	Tobacco and/or nicotine containing product
ULN	Upper limit of the normal range
ULOQ	Upper limit of quantification
vs	Versus
WHO	World Health Organization

Confidentiality Statement

Data and information contained in this document are considered to constitute trade secrets and confidential commercial information, and the legal protections provided to such trade secrets and confidential information are hereby claimed under the provisions of applicable law. No part of this document may be publicly disclosed without the written consent of Philip Morris Products S.A

Explanation of Terms

The following special terms are used in this protocol:

Alternate subjects	Subjects who have signed the ICF, have met the inclusion and exclusion criteria, and have been enrolled, but have not been randomized due to a sufficient number of subjects available for randomization at that time. In case the Admission Day-2 of the following group does not exceed the 28-day Screening period, to qualify for randomization, alternate subjects have to repeat the Admission visit to re-confirm their eligibility.
Cigarette(s) (CIG)	The term 'CIG' refers to commercially available regular or menthol cigarettes (manufactured) and excludes hand-rolled cigarettes, cigars, pipes, bidis, and other nicotine-containing products.
Early termination	Premature termination of exposure to the Investigational Product after the start of the Exposure period in the confinement setting.
End of study (EOS)	The EOS for a randomized subject is defined as the completion of the 3-day Safety follow-up period either after Discharge on Day 6, or after the date of early termination of the subject. The EOS of the entire study is the end of the Safety Follow-up Period for the last subject.
Randomization	Allocation of the respective product at any time on Day -1 utilizing an interactive web and voice response system (IxRS). On Day 1, the subjects will be individually informed about the product they are randomized to prior to the first product use.
Screening failure	All subjects that are not enrolled are considered as screen failures. Re-screening of subjects who did not meet any entry criteria will not be permitted.

Confidentiality Statement

Data and information contained in this document are considered to constitute trade secrets and confidential commercial information, and the legal protections provided to such trade secrets and confidential information are hereby claimed under the provisions of applicable law. No part of this document may be publicly disclosed without the written consent of Philip Morris Products S.A.

1. Ethics and Regulations

1.1 Independent Ethics Committee (IEC) Approval

Prior to the start of the study, the clinical study protocol, together with its associated documents (informed consent form [ICF] including the subject information sheet, subject recruitment procedures [e.g., advertisements], written information to be provided to the subjects, Investigator's brochure [IB], available safety information, curriculum vitae of the Principal Investigator(s) (PI(s)) and designee(s) and/or other evidence of qualifications and any other documents requested by an Independent Ethics Committee [IEC]), will be submitted for review and approval to the relevant IEC. The IEC shall be appropriately constituted and perform its functions in accordance with the International Council for Harmonization of Technical Requirements for Pharmaceuticals for Human Use (ICH) Guidance for Good Clinical Practice (GCP) [2] and local requirements, as applicable.

In accordance with GCP, a written confirmation of the IEC approval should be provided to the Sponsor. This should identify the study (name of the PI(s) and designee(s), study number, and title) and the documents that have been approved by the IEC, with dates and version numbers, as well as the date of approval. The composition of the IEC, including the name and occupation of the chairperson, will be supplied to the Sponsor together with a GCP compliance statement.

The written approval from the IEC will be filed in the Principal Investigator file, and a copy will be filed in the study master file at the Sponsor or designated organization. The study must not start at a site before the Sponsor has obtained written confirmation of favorable opinion/approval from the concerned IEC.

Any substantial change or addition to this protocol will require a written protocol amendment that must be approved by the Sponsor and the Principal Investigator(s). All amendments will be submitted to the IEC, and substantial amendments will only be implemented after approval by the IEC.

These requirements for approval should in no way prevent any action from being taken by the PI(s) or designee(s) or by the Sponsor to eliminate immediate hazards to the subjects. If such a change to the protocol is felt to be necessary by the PI(s) or designee(s), and is implemented for safety reasons, the Sponsor and the IEC should be informed immediately. The PI(s) is(are) responsible for local reporting (e.g., to the IEC) of serious adverse events (SAEs) that occur during the study, according to local regulations.

Relevant safety information will be submitted to the IEC during the study in accordance with national regulations and requirements.

Medically qualified study personnel will be available during the study.

Confidentiality Statement

Data and information contained in this document are considered to constitute trade secrets and confidential commercial information, and the legal protections provided to such trade secrets and confidential information are hereby claimed under the provisions of applicable law. No part of this document may be publicly disclosed without the written consent of Philip Morris Products S.A.

